Dural tear/injury	Yes 	No 				
Nerve root injury	Yes 	No 				
Other Adverse Events (Describe event below)			Severity	Relatedness	Action Taken	Outcomes

Clinical Site Number:

Subject Number:

Case Report Form
Integrity Implants FlareHawk® Study
 Post-Operative Adverse Event Log

POST-OPERATIVE ADVERSE EVENT (AE) LOG **No AEs Recorded**

If Adverse Events have occurred, check “yes” or “no” for each event listed below. If “yes” is marked for an Adverse Event below, please complete all of the columns to the right.

Adverse Events	Yes / No		Onset Date	Resolution Date	Severity	Relatedness	Action Taken	Outcomes
			MM/DD/YYYY	MM/DD/YYYY	1- None 2- Mild 3- Moderate 4- Severe 5- Death	1- Device related 2- Procedure related 3- Not related	1- None 2- Medication/ Therapy 3- Revision Surgery 4- Additional Surgery 5- Other	1- Resolved 2- Ongoing at 12-month (+/- 3 month) Follow-up 3- Unknown
Infection	Yes 	No 	/ /	/ /				
Donor site pain	Yes 	No 	/ /	/ /				
Complex regional pain syndrome	Yes 	No 	/ /	/ /				
Urinary retention/difficulty	Yes 	No 	/ /	/ /				
Ipsilateral or contralateral radiculopathy	Yes 	No 	/ /	/ /				
Device component breakage/fracture	Yes 	No 	/ /	/ /				
Device or device component migration/retropulsion	Yes 	No 	/ /	/ /				
Device complication (e.g. loss of expansion)	Yes 	No 	/ /	/ /				
Device subsidence	Yes 	No 	/ /	/ /				
Loss of fixation	Yes 	No 	/ /	/ /				
Non-union	Yes 	No 	/ /	/ /				
Vertebral fracture	Yes 	No 	/ /	/ /				
Adjacent segment disease	Yes 	No 	/ /	/ /				

Clinical Site Number:

Subject Number:

Case Report Form
Integrity Implants FlareHawk® Study
 Post-Operative Adverse Event Log

POST-OPERATIVE ADVERSE EVENT (AE) LOG Continued

No AEs Recorded

Please complete all columns below if additional Adverse Events are recorded.

Other Adverse Events (Describe event below)	Onset Date MM/DD/YYYY	Resolution Date MM/DD/YYYY	Severity 1- None 2- Mild 3- Moderate 4- Severe 5- Death	Relatedness 1- Device related 2- Procedure related 3- Not related	Action Taken 1- None 2- Medication/ Therapy 3- Revision Surgery 4- Additional Surgery 5- Other	Outcomes 1- Resolved 2- Ongoing at 12-month (+/- 3 month) Follow-up 3- Unknown
	/ /	/ /				
	/ /	/ /				
	/ /	/ /				
	/ /	/ /				
	/ /	/ /				

Clinical Site Number: Subject Number:

Case Report Form
Integrity Implants FlareHawk® Study
Radiographic Reviewer

CRF TO BE COMPLETED BY RADIOGRAPHIC REVIEWER ONLYDATE OF X-RAY: / /
MM DD YYYY**RADIOGRAPHS**X-ray views evaluated (check all that apply): AP Lateral Flexion/Extension **RADIOGRAPHS**

Using the Bridwell-Lenke grading system, what is the X-ray fusion status at L2 - L3?	Grade 1	
	Grade 2	
	Grade 3	
	Grade 4	
NA – Subject not implanted with FlareHawk device at L2-L3		

Using the Bridwell-Lenke grading system, what is the X-ray fusion status at L3 – L4?	Grade 1	
	Grade 2	
	Grade 3	
	Grade 4	
NA – Subject not implanted with FlareHawk device at L3-L4		

Using the Bridwell-Lenke grading system, what is the X-ray fusion status at L4 – L5?	Grade 1	
	Grade 2	
	Grade 3	
	Grade 4	
NA – Subject not implanted with FlareHawk device at L4-L5		

Using the Bridwell-Lenke grading system, what is the X-ray fusion status at L5- S1?	Grade 1	
	Grade 2	
	Grade 3	
	Grade 4	
NA – Subject not implanted with FlareHawk device at L5-S1		

Was any magnification adjustment used by the radiographic reviewer to grade fusion status? Yes No

If "Yes", describe below: _____

APPROVAL

Reviewer Signature: _____

Date: _____

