The study case report form (CRF) is the primary data collection instrument for the study. All data requested on the CRF must be recorded. All missing data must be explained. If a space on the CRF is left blank because the procedure was not done or the question was not asked, write "N/D". If the item is not applicable to the individual case, write "N/A". All entries should be printed legibly in black ink. If any entry error has been made, to correct such an error, draw a single straight line through the incorrect entry and enter the correct data above it. All such changes must be initialed and dated. DO NOT ERASE OR WHITE OUT ERRORS. For clarification of illegible or uncertain entries, print the clarification above the item, then initial and date it. The investigator will be responsible for maintaining adequate, accurate CRFs to guarantee the proper interpretation of the data.

4.3 Data to be Collected:

After confirming inclusion in the study based on the above inclusion and exclusion criteria, data collection from the subject record will include the following, as available:

1. Demographics:

- Age
- Gender at birth
- Diagnosis
- BMI
- Co-morbid conditions
 - Hypertension
 - Diabetes
 - Obesity (BMI \geq 30)
 - Hypercholesterolemia
 - Coronary Heart Disease
 - Hypothyroidism
 - Active or history of cancer
 - Other
- Smoking Status

2. Operative data:
 - Date of Surgery
 - Surgical level(s)
 - Description of all implants and graft materials used, including supplemental fixation if described
 - PLIF or TLIF approach
 - Open, mini-open, or minimally invasive procedure
 - Estimated blood loss
 - Length of surgery
 - Fluoroscopic exposure time
 - Intraoperative device- or procedure-related adverse events
 - Device component breakage/fracture
 - Device malfunction
 - Dural tear/injury
 - Nerve root injury
 - Device-related delay of surgery
 - Retained foreign body
 - Other
 - Length of hospitalization
3. Patient reported outcomes surveys at preoperative baseline and each follow-up:
 - Visual Analog Scale (VAS) back and/or leg – Self Administered Questionnaire
 - Oswestry Disability Index (ODI) - Self Administered Questionnaire
4. Radiographs:
 - Intraoperative post-implantation Lateral and AP X-rays of the lumbar spine
 - 12 months (+/- 3 months) follow-up Lateral, AP, and Flexion-Extension X-rays of the lumbar spine
5. Post-operative device- or procedure-related adverse events
 - Infection
 - Donor site pain
 - Complex Regional Pain Syndrome

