Radiographs will be evaluated by up to three reviewers (two primary reviewers and an adjudicator, as necessary, to evaluate any contradicting reviews by the primary reviewers). Reviewers will be 3rd party board-certified orthopedic surgeons, neurosurgeons, or radiologists.

Fusion status will be determined according to the Bridwell-Lenke grading system [Bridwell and Lenke et al, 1995], with grades 1-2 accepted as “Fused” and grades 3-4 accepted as “Not Fused”:

- Grade 1: Fused with remodeling and trabeculae present
- Grade 2: Graft intact, not fully remodeled and incorporated, but no lucency present
- Grade 3: Graft intact, potential lucency present at top and bottom of graft
- Grade 4: Fusion absent with collapse/resorption of the graft

6.2 Data Analysis:

Primary outcome:

The proportion of levels achieving arthrodesis at 12 months (+/- 3 months) will be summarized as a percentage and 95% confidence interval, based on the Wilson score method for binomial confidence intervals.

Secondary outcomes:

Continuous variables, such as baseline demographics and change in patient-reported outcomes from preoperative baseline to 12 months, will be summarized using mean, standard deviation, minimum and maximum values. Paired t-test or a non-parametric equivalent (if data does not satisfy assumptions of normality) will be used to determine if changes in VAS or ODI scores are statistically significant from preoperative baseline to 12 months (+/- 3 months) follow-up. Responder analyses for changes in patient-reported outcomes at 12 months (+/- 3 months) will be conducted using minimum clinically important differences (MCID). Significant clinical improvements from preoperative baseline to 12 months (+/- 3 months) follow-up will be determined on a per-patient basis using the following MCID values:

- Improvement in ODI \geq 10 points [Ostelo et al. 2008]
- Improvement in VAS leg pain \geq 15 points [Ostelo et al. 2008]
- Improvement in VAS back pain \geq 15 points [Ostelo et al. 2008]

The proportion of patients with improvements exceeding the MCID values will be summarized as a percentage and 95% confidence interval.

Sub-group analyses will be performed based on the implant version (split-shim vs. “Version B”), history of previous surgery at the index level, patient co-morbidities, and demographic variables.

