Hypercholesterolemia Coronary Heart Disease Hyperthyroidism
Active Cancer History of Cancer
If checked, type of cancer: _____ If checked, type of cancer: _____
None recorded **VISUAL ANALOG SCALE (VAS)**Please enter the VAS score as documented at the baseline visit in the medical records for the level of **RIGHT LEG** pain.VAS **Right Leg** Pain Score: _____ Not Recorded Please enter the VAS score as documented at the baseline visit in the medical records for the level of **LEFT LEG** pain.VAS **Left Leg** Pain Score: _____ Not Recorded Please enter the VAS score as documented at the baseline visit in the medical records for the level of **BACK** pain.VAS **Back Pain** Score: _____ Not Recorded

Clinical Site Number: Subject Number:

Case Report Form
Integrity Implants FlareHawk® Study
Baseline Data – Visit 1

OSWESTRY DISABILITY INDEX (ODI)

Please transcribe answers directly from the patient's medical record.
(Circle score for each section recorded)

Not Recorded

Section 1 – Pain Intensity	
0	I have no pain at the moment
1	The pain is very mild at the moment
2	The pain is moderate at the moment
3	The pain is fairly severe at the moment
4	The pain is very severe at the moment
5	The pain is the worst imaginable at the moment

Section 4 – Walking	
0	Pain does not prevent me walking any distance
1	Pain prevents me from walking more than 1 mile
2	Pain prevents me from walking more than ½ mile
3	Pain prevents me from walking more than 100 yards
4	I can only walk using a cane or crutches
5	I am in bed most of the time

Section 2 – Personal Care (washing, dressing, etc.)	
0	I have no pain at the moment
1	The pain is very mild at the moment
2	The pain is moderate at the moment
3	The pain is fairly severe at the moment
4	The pain is very severe at the moment
5	The pain is the worst imaginable at the moment

Section 5 – Sitting	
0	I can sit in any chair as long as I like
1	I can only sit in my favorite chair as long as I like
2	Pain prevents me from sitting more than one hour
3	Pain prevents me from sitting more than 30 minutes
4	Pain prevents me from sitting more than 10 minutes
5	Pain prevents me from sitting at all

Section 3 – Lifting	
0	I can lift heavy weights without extra pain
1	I can lift heavy weights but it gives extra pain
2	Pain prevents me from lifting heavy weights off the floor, but I manage if they are conveniently placed e.g. on a table

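### The baseline case report form prints a different thyroid condition from the one in section 4.3 and omits two other listed items; protocol and form need reconciling

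*Combined protocol and SAP*

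**What the plan says.** **Co-morbidities.** Section 4.3 of Attachment A, item 1, lists seven named conditions and then Other. The sixth is "Hypothyroidism" and the seventh is "Active or history of cancer". The baseline CRF (Visit 1, Comorbid Conditions) starts with the same first three conditions, continues with "Hypercholesterolemia Coronary Heart Disease Hyperthyroidism", gives two cancer boxes (active and past), and ends with "None recorded".

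**Intraoperative events.** Section 4.3, item 2, has a sub-list headed "Intraoperative device- or procedure-related adverse events". It names six events, among them "Retained foreign body", and then Other. The pre-printed rows of the Intra-Operative AE Log end at "Nerve root injury"; free-text rows for other events follow.

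**Use in the analysis.** Section 9.2 of the protocol and section 6.2 of Attachment A plan subgroup analyses by implant version and by "history of previous surgery at the index level, patient co-morbidities, and demographic variables". Both also plan to report each type of adverse event as a rate with a 95% confidence interval and to compare it with published rates. Section 4.2 makes the CRF the main instrument for collecting the study's data.

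**The concern.** In a chart review, the form largely decides what enters the database. If the protocol names a condition and the form prints a different one, the named condition has no box. Because the open line is also missing, there is no fallback within the co-morbidity block. At stake is a covariate for a planned subgroup analysis: what 4.3 says was collected would not be what was collected, and conditions outside the printed list would be lost.

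The planned quality checks are unlikely to reveal this. Double data entry (4.4) confirms that the database matches the form. Queries (4.4) respond to missing, implausible or inconsistent entries, and an unticked box is none of these. Source verification (4.5) compares recorded entries with the chart, and for a hypothyroid patient an unticked hyperthyroidism box is correct. The fault lies in the form, not in how it is filled in.

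The retained-foreign-body item raises a smaller question. Its rate would rest on an unprompted free-text entry, while the other five named intraoperative events have a field of their own.

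**Working it through.** The check is an item-by-item comparison of section 4.3 with the CRF pages.

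| Section 4.3, co-morbidities | Baseline CRF, Visit 1 | Match |
|---|---|---|
| Hypertension | box | yes |
| Diabetes | box | yes |
| Obesity | box | yes |
| Hypercholesterolemia | box | yes |
| Coronary heart disease | box | yes |
| Hypothyroidism | hyperthyroidism box | **no** |
| Cancer, active or past | two boxes | yes |
| Other | nothing | **no** |

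Six of the eight entries match, or six of the seven named conditions. Both thyroid words are intact in the text and the five conditions before them run in the same order, so the difference is not an artefact of text extraction.

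| Section 4.3, intraoperative events | Where the CRF collects it |
|---|---|
| Breakage or fracture | row on Intra-Operative AE Log |
| Malfunction | row on the log |
| Dural tear or injury | row on the log |
| Nerve root injury | row on the log |
| Device-related delay | own field, Surgery form (Visit 2) |
| Retained foreign body | **no field**; free text only |
| Other | free-text rows on the log |

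Five of the six named events have a field. The Post-Operative AE Log has no row for a retained foreign body either.

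**Consequence for one patient.** Take a patient with hypothyroidism and nothing else on the printed list. No box matches and there is no open line. The block can be left blank, or the no-condition box can be ticked. Either way, the database does not show the condition.

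**What missed capture could mean for the event.** The sample size sections (protocol section 6.1; Attachment A section 3.6) state that 100 subjects allow detection of events with probability 1.6% at 80% power. To reproduce that figure: P(at least one event) = 1 − (1 − p)^n = 1 − 0.984^100 = 80.1%, which agrees. If only a fraction s of true events is written down, the chance becomes 1 − (1 − 0.016s)^100. The documents give no value for s, so the range below is an assumption:

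- s = 0.9: 1 − 0.9856^100 = 77%
- s = 0.75: 1 − 0.988^100 = 70%
- s = 0.5: 1 − 0.992^100 = 55%

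These figures illustrate sensitivity to s for an event whose true rate is 1.6%. They do not estimate a loss in this study, and the documents give no expected rate for this event.

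**The case against.** The strongest reply is that the practical effect is small and partly conjectural. Most of that reply stands, and it rules out several stronger readings that a reader might infer.

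- *All co-morbidity subgroups are recorded wrongly.* They are not: six of seven named conditions match.
- *The thyroid subgroup would be the opposite condition.* Sections 9.2 and 6.2 name co-morbidities only in general terms and specify no thyroid contrast.
- *Every hypothyroid patient is coded as not having the condition.* The form leaves the condition uncollected. A false entry of no co-morbidity is possible only for patients with nothing else on the list, and whether a site would make it is a guess.
- *The retained-foreign-body rate is biased low.* The event can be written on the log with severity, relatedness, action and outcome. The Visit 2 form also asks whether any intraoperative event occurred, asks about instrument problems, and has a comments field that invites safety concerns. The log's checklist is completed only once an event has been reported, so the difference in prompting is narrow. Under-ascertainment or inconsistent coding is a fair worry; a bias is not shown.
- *It is a missing device event.* The heading in 4.3 covers device- or procedure-related events, so that label is too specific.
- *The form is plainly the document in error.* Nothing states which thyroid condition was intended.

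It could also be said that site training on the protocol and on-site source verification (4.5) give some protection. That carries less weight: a check of recorded entries need not expose a field that does not exist. What survives is the mismatch itself, which is certain from the text, and the fact that one affected item feeds a planned subgroup factor.

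**Conclusion.** The concern holds as a discrepancy between protocol and form, of minor severity. As printed, the baseline CRF cannot record the thyroid condition named in 4.3 or any unlisted co-morbidity. One named intraoperative event lacks a row but has a free-text route.

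Its size, counted in items, is one of seven named co-morbidities replaced, one open entry missing, and one of six named intraoperative events unprompted. The number of patients affected depends on prevalence and on how sites fill in the page, and the documents give neither.

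The primary fusion outcome, the VAS and ODI change and responder analyses, and the sample size do not use these fields and are unaffected. The conclusion assumes only that the CRF pages attached to the plan are the ones sites use.

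**What to change.** 1. Reconcile the thyroid term between section 4.3 and the baseline CRF. The form implements the protocol, so by default it should follow 4.3, with the sponsor confirming which condition was intended.
2. Add an Other (specify) line to the co-morbidity block.
3. Add a yes/no row for retained foreign body to the Intra-Operative AE Log.
4. Where the present pages have already been completed, re-check these three items against the chart at the on-site source verification planned in section 4.5.

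The cost is a revision of three CRF fields and a short chart re-check. No new patients or procedures are needed.

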3	Pain prevents me lifting heavy weights, but I can manage light to medium weights if they are conveniently positioned
4	I can lift very light weights
5	I cannot lift or carry anything at all

Section 6 – Standing	
0	I can stand as long as I want without extra pain
1	I can stand as long as I want but it gives me extra pain
2	Pain prevents me from standing more than 1 hour
3	Pain prevents me from standing more than 30 minutes
4	Pain prevents me from standing for more than 10 minutes
5	Pain prevents me from standing at all

Clinical Site Number:

Subject Number:

Case Report Form
Integrity Implants FlareHawk® Study
 Baseline Data – Visit 1

OSWESTRY DISABILITY INDEX (ODI) Continued

Please transcribe answers directly from the patient's medical record.
 (Circle score for each section recorded)

Not Recorded

Section 7 – Sleeping	
0	My sleep is never disturbed by pain
1	My sleep is occasionally disturbed by pain
2	Because of pain I have less than 6 hours sleep
3	Because of pain I have less than 4 hours sleep
4	Because of pain I have less than 2 hours sleep
5	Pain prevents me from sleeping at all

Section 8 – Sex Life (if applicable)	
0	My sex life is normal and causes no extra pain
1	My sex life is normal but causes some extra pain
2	My sex life is nearly normal but is very painful
3	My sex life is severely restricted by pain
4	My sex life is nearly absent because of pain
5	Pain prevents any sex life at all

Section 9 – Social Life	
0	My social life is normal and gives me no extra pain
1	My social life is normal but increases the degree of pain
2	Pain has no significant effect on my social life apart from limiting my more energetic interests e.g. sports
3	Pain has restricted my social life and I do not go out as often
4	Pain has restricted my social life to my home
5	I have no social life because of pain

Section 10 – Traveling	
0	I can travel anywhere without pain
1	I can travel anywhere but it gives me extra pain
2	Pain is bad but I manage journeys over two hours
3	Pain restricts me to journeys of less than one hour
4	Pain restricts me to short necessary journeys under 30 minutes
5	Pain prevents me from traveling except to receive treatment

Clinical Site Number: Subject Number: **Case Report Form**
Integrity Implants FlareHawk® Study
Surgery – Visit 2

Page 1 of 3

VISIT 2 – SURGERYDATE OF SURGERY: / /
MM DD YYYYTotal Operative Time: min.

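### The ODI case report form pages take section scores only, so a chart that holds just an ODI total has no field and would drop out of the ODI analyses

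*Combined protocol and SAP*

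**What the plan says.** Change in ODI from baseline to 12 months is a named secondary outcome (clinical protocol 4.3; Attachment A 3.4). Clinical protocol 9.2 and Attachment A 6.2 plan a mean change, a paired test and a responder analysis with a cut-off of at least 10 points.

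The data come from charts, as available (Attachment A 4.3). Each ODI form lists ten sections scored 0 to 5. The instructions are "Please transcribe answers directly from the patient's medical record" and "Circle score for each section recorded". The only other entry is a Not Recorded box. No ODI page has a field for a total or a percent. The VAS items on the same set of forms ask for the score as documented in the medical record.

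One section is optional on every form: "Section 8 – Sex Life (if applicable)". Its top answer, scored 5, is "Pain prevents any sex life at all".

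Neither analysis section gives a formula for the ODI total, its scale, its denominator, or a rule for a section answered at only one visit. The cut-offs for ODI and both VAS scores carry a greater-or-equal sign, but the summary sentence then reads "The proportion of patients with improvements exceeding the MCID values will be summarized as a percentage and 95% confidence interval".

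**The concern.** The analyses need an ODI total, and the forms can only build one from section answers. A chart may hold the total alone, because the clinic scored the questionnaire and filed only the result. Such a chart contains a usable outcome that the form cannot accept. A change score needs both visits, so a total-only record at either visit is enough to remove the patient.

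If recording practice differs by site, the loss would fall by site and not at random. The population sections (clinical protocol 4.4; Attachment A 3.5) promise homogeneous data collection before sites are pooled. Attachment A 4.1 extends the date range when fewer than 100 patients have 12-month follow-up data. It does not say that ODI must be among those data, so the extension need not make up the shortfall.

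A secondary matter is that, without a stated scoring rule, a section left blank at one visit can move the total when disability has not changed.

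**Working it through.** No stated sample size, interval or power figure rests on the ODI, so there is no plan figure to reproduce.

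**Entry routes, side by side**

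| Chart contains | VAS | ODI |
|---|---|---|
| Section answers | not applicable | circle each score |
| A score or total only | enter as documented | no field; only Not Recorded fits |
| Nothing | Not Recorded | Not Recorded |

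The middle row is the gap. Its size is unknown. Let *t* be the share of patients whose ODI is total-only at either visit, and take the 100 patients with 12-month data that the plan aims for. The ODI analyses then keep 100 × (1 − *t*) of them. For assumed values of *t* of 5%, 10% and 20%, that is 95, 90 and 80. If one of three equally sized sites charted totals only (also an assumption), about 100/3 ≈ 33 patients would be missing, all from that site.

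**Effect of a blank Section 8**

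Inputs: ten sections, each 0-5, so the raw maximum is 10 × 5 = 50 (from the forms); cut-off 10 points (9.2 and 6.2). The 0-100 scale is an assumption, because the plan gives none. Take a patient with no true change whose Section 8 score *x* is recorded at baseline and blank at 12 months. Let S be the sum of the other nine sections.

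- Fixed denominator, sum doubled: apparent gain = 2(S + *x*) − 2S = 2*x*. For *x* = 0 to 5 this is 0, 2, 4, 6, 8, 10.
- Raw 0-50 sum: apparent gain = *x*, at most 5.
- Scored on answered sections: apparent gain = 2(S + *x*) − 100S/45 = 2*x* − (2/9)S. With S = 18 and *x* = 5, the score goes from 46 to 40, a gain of 6. It reaches 10 only when *x* = 5 and S = 0.
- Both visits scored on the nine sections answered at both: apparent gain = 0.

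If Section 8 is blank at baseline instead, the fixed-denominator error has the opposite sign and can hide a real response of the same size.

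**At least 10, or more than 10**

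On a doubled sum the ODI moves in steps of 2, so a change of exactly 10 can occur. With a normal approximation on that grid, mean improvement 20 and SD 18 (assumed), P(exactly 10) = Φ((11 − 20)/18) − Φ((9 − 20)/18) = Φ(−0.500) − Φ(−0.611) ≈ 0.038. Over means of 15-25 and SDs of 15-20 it is 0.030 to 0.050.

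**The case against.** Collecting section answers is a defensible choice, because every total is then built the same way and can be verified against source. Attachment A requires missing data to be explained (4.2), sends gaps to query (4.4) and has the monitor check forms against charts (4.5), so a charted total might come to light. That stands as far as it goes, but none of these steps gives the total a place in the data, and a query cannot recover section answers that the chart lacks. The entry rule that begins "If the item is not applicable to the individual case, write" governs what to write on the form, not how to score it.

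A scoring rule may also sit in the data processing plan cited in Attachment A 4.4, which is not among the documents, and analysts might apply conventional scoring anyway. That is fair. The claim is limited to the supplied protocol, analysis sections and forms.

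Three stronger readings are tempting and are not supported.

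- A reader might infer that valid ODI data are being discarded. The documents do not say that any chart holds only a total.
- A reader might infer that a skipped question will produce false responders. For a patient with no real change, that needs a doubled sum over a fixed 50, a Section 8 score of 5 at baseline, a blank at 12 months, and the 'at least 10' reading. A patient with all ten sections at 4 would go only from 80 to 72, which is not a response. A smaller skipped score reaches 10 only when added to a real gain.
- A reader might infer that doubt over the scale shifts the responder rate from about 73% to 52% (10 points on 0-100 against 10 raw points, which is 20 on 0-100). Those figures rest wholly on an assumed mean of 20 and SD of 18. The raw-scale problem and the 10-point artefact also cannot occur together.

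**Conclusion.** The point holds for the forms: total-only ODI charts have no entry route, although VAS scores do, and with the forms followed as written those patients leave the ODI analyses. The number affected cannot be known from the documents. The primary fusion outcome and the sample size are untouched; what is at risk is one named secondary outcome, which also bears on the disability part of the primary hypothesis.

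The missing scoring rule is a supporting clarification. Its worst effect is 10 points in either direction for an individual patient, under a fixed denominator that the plan never adopts. The conflict between the greater-or-equal cut-offs and "The proportion of patients with improvements exceeding the MCID values" is real but small: about 3-5% of patients for ODI under the assumed distributions. It applies equally to both VAS cut-offs.

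**What to change.** 1. On all three ODI forms, add a line such as: 'Total ODI as charted: ____ (percent / out of 50)'. Use it only when section scores are not in the chart, and flag those records.
2. In clinical protocol 9.2 and Attachment A 6.2, state that ODI = 100 × sum of answered sections / (5 × number answered), with a stated minimum number of answered sections. State that change uses the sections answered at both visits whenever section scores exist.
3. State that total-only charts use the charted percent, or the out-of-50 total doubled, and add a sensitivity analysis that leaves them out. A charted total may hide a blank section, so the same-sections rule cannot protect these patients.
4. In both analysis sections, replace *exceeding* with 'at or above' for the ODI and both VAS cut-offs.

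The cost is one field per form and a few sentences. The downside is that charted totals cannot be checked section by section, which the flag and the sensitivity analysis address. Separately, Section 2 on all three forms repeats the answer options of Section 1; this should be corrected at the same time, because it affects any total built from sections.
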